In each CNC about 20 children are expected to suffer from moderate malnutrition.

The study hypothesis is that there will be no difference in improvement between intensive nutrition education group and less intensive education group in proportions improving from moderate malnutrition receiving nutrition education. The study will disprove the hypothesis if a 15% difference is detected with statistical significance.

$$\text{Using formula } n = \frac{p_1(1-p_1) + p_2(1-p_2)}{(p_1 - p_2)^2} (z_{\alpha} + z_{\beta})^2$$

(Reference: G W Snedecor and WG Cockran. Statistical Methods in Medical sciences. Oxford Publications 6th edition 1968, pp 111-114). Where p_1 is proportion of reduction of moderate malnutrition in intensive nutrition intervention group and p_2 is reduction in proportion of malnutrition in less intensive education group and $(z_{\alpha} + z_{\beta})$ is the function of level of significance and power of the statistical test.

$p_1=0.5$ and $p_2=0.35$

where z_{α} = level of significance at 5%, =1.96

and z_{β} = power of the study 90%, =1.28

where $(p_1 - p_2)$ = difference of proportion moving to mild malnutrition between control and intervention group.

$$n = \frac{0.5 \times 0.5 + 0.35 \times 0.65}{(0.15)^2} \times 10.5 = 222.$$

Taking a cluster effect of the design as the children will be selected from CNC s this is increased to $222 \times 1.5 = 333$. with a drop out possibility of 10%, it will be about 366 children in each group.

Total sample size will be $366 \times 2 = 732$ or 750 subjects.

Sample size for preventive study group:

Assumption is that mildly malnourished children will usually slip into moderate malnutrition without any nutrition education but with less intensive nutrition education, they will not slip into malnutrition. The study will be interested to detect a difference of 20% with a 5% probability and

90% power.

[figure not shown]
To detect this 20% difference the number of mildly malnourished children in two study groups will be $(121 \times 2) = 242$. The cluster effect of randomization by CNCs will be controlled by multiplying the number by a factor of 1.5 i.e. $242 \times 1.5 = 363$ for mildly malnourished groups and possible drop out (10%) can be covered with a total number of $(190 \times 2) = 380$ subjects.

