As almost 80% of the 6-9 month old infants will be included in mild and moderate groups, rest 20% who are well nourished will be studied with less intensive education for preventive approach. There will be $(50 \times 2) = 100$ infants in 6-9 month old group to receive either less intensive education on complementary feeding or no education. These well nourished infants will be analyzed separately to see if less intensive education on complementary feeding prevents them from falling to mild or moderate malnutrition.

Selection and randomization procedure: (Tables 1,2,3)

For management approach the number of subjects will be 375 in each group and a total of 750 children will be selected from 40 CNCs from 4 divisions. One thana will be randomly selected from each Division, and two unions will be randomly selected from each thana, and 5 CNS will be randomly selected from each union. From a total of $(5 \times 2 \times 4) = 40$ CNCs, 20 will be allocated for intensive education and 20 will be randomly allocated for less intensive education.

To avoid contamination for the control groups with no nutrition education in the preventive approach, 8 additional CNCs will be randomly selected one from each union of the four divisions. Finally in each union 5 CNCs will be under either intensity of education and one CNC will be with no education. A diagram is given below:

LINE : Less intensive nutrition education, INE : Intensive nutrition education

Table 1

Sample selection

Subjects	Intensive education	Less intensive education	No education	Total
Moderately malnourished	375	375	---	750
Mildly malnourished	---	190	190	380
6-9 months old infants	---	50	50	100
CNCs	20	20	8	48

Table 2

RANDOMIZATION PROCEDURE

[figure not shown]
[figure not shown]

Table 3

Selection procedure

Randomization procedure:

(a) Total number recruited moderately malnourished children are 750. They will be selected equally from 40 CNC's in two study groups. Individual child will not be randomized but the children in each CNC as a group will be allocated randomly to either of the two study groups according to a random number table. Identified 5 CNC's in each union will be randomly allocated by their identification numbers to one of the two study groups.

(b) In the preventive group, mildly malnourished children will be randomized by CNCs for less intensive nutrition education or no nutrition education.

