Data will be double entered in a microcomputer within a week of data collection. The field supervisors will visually check data before sending for entry into the computer. Any error, discrepancy or omission found during data entry will be reported to the investigators without delay. Data will be entered into microcomputer using SPSS Windows's program. Data on weight gain, frequency and introduction of complementary feeding will be compared between experimental groups. Complementary feed introduction and regularity will be compared among 6-9 month age groups in education and control groups. Comparability between intervention and control groups will be assessed by baseline characteristics such as age sex, nutritional status, socioeconomic characters, feeding practices, etc. Continuous variables will be assessed for normal distribution. T test will be performed to compare data of normal distribution; otherwise non-parametric test will be used. Chi-squared test will be performed for categorical variables, Multiple regression analysis will be done with weight gain as dependent variable and intervention and potential confounding variables such as age, sex, SES, baseline nutritional status, infection as independent variables. Separate analysis will be performed for periods of intervention, reinforcement and observation.

Compliance of nutrition education will be measured at 2 weekly observation period (already mentioned). Compliance will be measured as process indicator. Comparison of compliance will only

be done at the end of the study so that the investigators will have no idea about which group is more a less compliant. Therefore, these will be little change of introduction of bias due to non-compliance, effect of intensive or less intensive nutrition education will be compared as a whole. So complain will be seen as a factor of nutrition education with given intensive. Analysis of compliance data will be done by relating to the outcome effect of nutritional status and can be compared between two education groups.

Analysis of qualitative data

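### CNCs are allocated within unions of four thanas, but the named tests work on children and use neither the CNC nor the thana: they reject too often, and a CNC-level analysis should also carry a thana term

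*Protocol*

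**What the plan says.** **Design.** The protocol's Selection and randomization procedure and Site selection sections take one thana from each of four divisions, two unions from each thana and six CNCs from each union. For intensive (INE) against less intensive (LINE) education, "Identified 5 CNC's in each union will be randomly allocated by their identification numbers to one of the two study groups", giving 20 CNCs per arm over the whole trial. For the no-education controls, "8 additional CNCs will be randomly selected one from each union of the four divisions". Children are not randomised individually.

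**Sample size.** The section recognises clustering: "Taking a cluster effect of the design as the children will be selected from CNC s this is increased to" 333 per arm, a factor of 1.5. The test is set at "level of significance at 5%, =1.96" with "power of the study 90%, =1.28".

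**Analysis.** The Data Analysis section names a t test or non-parametric alternative, and then: "Chi-squared test will be performed for categorical variables, Multiple regression analysis will be done with weight gain as dependent variable", on intervention and "potential confounding variables such as age, sex, SES, baseline nutritional status, infection as independent variables". The CNC, union and thana appear in none of these.

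**The concern.** Two features of the design are absent from the analysis.

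- **The CNC is the unit of randomisation.** Children in one CNC share a health assistant, a setting and an allocation. A test that treats them as independent has a standard error that is too small. The factor of 1.5 buys extra children but does not correct the test.
- **The thana is a level within which arms are spread.** Any thana difference largely cancels from the arm contrast. An analysis that respects the CNC but omits the thana leaves that variance in its error, so its standard error is too large.

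Both sized comparisons are affected. Hypothesis (a) is that LINE works as well as INE, and it is to be rejected if a 15-point difference is significant. A false positive wrongly discards LINE, and low power wrongly endorses it. For LINE against no education, a false positive would credit the programme with a preventive effect that it does not have.

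**Working it through.** **1. The plan's own figure.** With proportions 0.50 and 0.35 and multiplier 10.5:

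(0.5×0.5 + 0.35×0.65)/0.15² × 10.5 = 0.4775/0.0225 × 10.5 = 222.8 (plan: 222).

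222 × 1.5 = 333; 333 × 1.1 = 366.3 (plan: 366); 366 × 2 = 732, raised to 750. The figure reproduces.

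**2. Implied ICC.** There are 375/20 = 18.75 children per CNC. From 1.5 = 1 + (18.75 − 1)ρ, ρ = 0.5/17.75 = 0.028. After 10% loss, m = 16.875 and ρ = 0.5/15.875 = 0.031. The protocol gives no ICC and no between-thana variance.

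**3. Effect of each omission, by formula.** Let s be the share of between-CNC variance lying between areas, with arms balanced within areas and n = 337.5 evaluable children per arm.

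- Variance factor that a CNC-level test without an area term works with: D0 = 1 + (m − 1)ρ.
- Variance factor of the actual contrast: D1 = (1 − sρ) + (m − 1)(1 − s)ρ.

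Worked case, ρ = 0.05 and s = 0.5: D0 = 1 + 15.875×0.05 = 1.794; D1 = 0.975 + 15.875×0.025 = 1.372. The standardised effect is 0.15/√(0.4775×1.372/337.5) = 3.40.

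| Analysis | Critical value on the true scale | False-positive rate | Power |
|---|---|---|---|
| Child-level, as named | 1.96/√1.372 = 1.67 | 9.4% | 95.8% |
| Child-level + area | 1.96×√(0.975/1.372) = 1.65 | 9.8% | 96.0% |
| CNC-level | 1.96×√(1.794/1.372) = 2.24 | 2.5% | 87.8% |
| CNC-level + area | 1.96 | 5% | 92.6% |

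With no area variance and a factor of exactly 1.5, the child-level test has a false-positive rate of 2[1 − Φ(1.96/√1.5)] = 11%.

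**4. Simulation with thana as the area.** 4,000 trials per cell, CNCs split 5:5 within each thana. INE v LINE: 40 CNCs of 17 children, 0.50 v 0.35. LINE v none: 20 CNCs of 9 children against 8 of 21, 0.30 v 0.50. The last pair is reconstructed from the plan's 121 per group: (0.21 + 0.25)/0.04 × 10.5 = 120.75.

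Child-level chi-squared against the same test stratified by thana (Mantel-Haenszel), power:

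| ICC, thana share | INE v LINE | LINE v none |
|---|---|---|
| 0.028, half | 96.8 v 96.8% | 95.6 v 95.7% |
| 0.05, half | 96.2 v 96.2% | 94.7 v 95.1% |
| 0.05, three quarters | 97.0 v 97.3% | 96.1 v 96.5% |
| 0.08, half | 94.3 v 94.6% | 93.5 v 93.9% |

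The thana term moves power by at most 0.4 point. False-positive rates are 6.6% to 13.1% without it and 7.0% to 13.7% with it.

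CNC-level weighted analysis, without against with thana, power:

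| ICC, thana share | INE v LINE | LINE v none |
|---|---|---|
| 0.028, half | 92 v 94% | 90 v 92% |
| 0.05, half | 86 v 91% | 85 v 88% |
| 0.05, three quarters | 88 v 95% | 87 v 92% |
| 0.08, half | 77 v 86% | 77 v 84% |
| 0.05, none | 82 v 82% | 81 v 81% |

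Where thanas differ, false-positive rates are 1.9% to 4.0% without the term and 4.1% to 5.4% with it. A separate run of the same design gave gains within 2 points of these. If the 20/20 split is not balanced by thana, the gain at ICC 0.05 with half between thanas is still about 4 points (84 v 88%; 85 v 89%).

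**The case against.** A reader might infer that omitting the union or thana makes the named tests conservative and costs them power. The documents do not support that. The tests as written contain no CNC-level step, so they err in the opposite direction, and adding thana to them gains almost nothing. The power loss belongs only to an analysis that already respects the CNC, which the protocol does not name.

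Other points on the plan's side:

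- *The covariate list is open, and an analysis plan not shown may add terms.* This holds for the regression, whose list is only illustrative. It does not help the t test and chi-squared test, which take no covariate and are named for the group comparisons.
- *Regional differences in outcome are not documented.* Correct. Primary objective (b) concerns the content of education messages by region, not recovery rates. The thana share is therefore an assumption, and at the ICC implied by the plan the gain is only about 2 points.
- *The split within unions is unclear.* Five CNCs cannot divide equally, and the allocation diagram is not shown. One sentence could even be read as each union having a single intensity. A thana term can be fitted under either reading, whereas a union term could coincide with the arm under the second.

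**Conclusion.** The point holds in two linked parts of unequal weight. The larger is that child-level tests ignore the randomised unit, giving false-positive rates of about 7% to 13% at ICCs of 0.028 to 0.08 where thanas differ. The smaller is conditional: once the CNC is respected, leaving out thana gives away about 2 points of power at ICC 0.028 and about 4 to 8 points at 0.05 to 0.08, with a false-positive rate of about 2% to 4% instead of 5%. The smaller part rests on half or more of the between-CNC variance lying between thanas; the protocol gives no figure for that share, nor any support for an ICC above 0.028. The plan should be changed, chiefly for the first part.

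**What to change.** In Data Analysis, state that INE v LINE and LINE v no education are analysed by a method that respects the CNC: either CNC-level summaries, or a mixed model or GEE with a small-sample correction. The correction matters most for the preventive comparison, which has only 8 control CNCs. Include thana as a 4-level fixed effect (3 indicators). Apply this both to weight gain and to the proportion changing nutritional grade. Prefer thana to the 8 unions: it uses 3 degrees of freedom rather than 7.

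The cost is a sentence or two of wording, since the CNC and thana of every child are known from the selection procedure. The CNC step needs no extra children if the factor of 1.5 is right: 337.5 evaluable per arm gives Φ(0.15/√(0.4775×1.5/337.5) − 1.96) = Φ(1.30), about 90% power. The thana term costs 3 degrees of freedom, under 1 point of power if thanas turn out alike.

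### Whole CNCs are allocated, but the named tests treat children as independent; at the plan's own design effect of 1.5, a nominal 5% test of INE against LINE has a true error of about 11%

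*Protocol*

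**What the plan says.** **Allocation.** Under Randomization procedure, item (a), the management comparison is allocated by centre: "Individual child will not be randomized but the children in each CNC as a group will be allocated randomly". Under Selection and randomization procedure, of 40 CNCs "20 will be allocated for intensive education and 20 will be randomly allocated for less intensive education". Item (b) does the same for prevention: "In the preventive group, mildly malnourished children will be randomized by CNCs for less intensive nutrition education or no nutrition education". Item (c) repeats it for well-nourished infants. Table 1 gives 20, 20 and 8 CNCs for intensive, less intensive and no education.

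**Sample size.** The management calculation multiplies 222 per group by 1.5 for the cluster effect. The preventive calculation uses the same factor and states: "The cluster effect of randomization by CNCs will be controlled by multiplying the number by a factor of 1.5".

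**Analysis.** The Data Analysis section names a t test for normally distributed data and a non-parametric test otherwise. It continues: "Chi-squared test will be performed for categorical variables, Multiple regression analysis will be done with weight gain as dependent variable". The regression covariates given as examples are age, sex, socioeconomic status, baseline nutritional status and infection. No CNC, union or thana term, centre-level summary, mixed model, GEE or robust variance appears anywhere in the protocol.

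**The concern.** The design and the analysis use different units. Children in one CNC share a health assistant, group teaching sessions and local food conditions, so their outcomes are likely to be correlated, and the factor of 1.5 concedes this. Enlarging the sample offsets the loss of power from that correlation, but only if the analysis also accounts for the CNC. A child-level t test or chi-squared test on clustered data still computes its standard error as if every child were independent. At a design effect of 1.5 that standard error is too small by a factor of sqrt(1.5) = 1.22.

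Two kinds of error follow. In the management comparison, the protocol rejects its no-difference hypothesis if a 15% difference reaches significance, so excess type I error produces false declarations that INE and LINE differ. Such declarations count against the hypothesis that the two are equally effective. In the preventive comparison, it produces false claims that LINE is better than no education, and there one side rests on 8 CNCs. The results are intended for immediate use by the national programme.

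**Working it through.** **Inputs from the protocol.** Two-sided 5% ("level of significance at 5%, =1.96"); power 90% (z = 1.28); proportions 0.50 and 0.35; design effect (DE) 1.5; dropout 10%; 375 children in 20 CNCs per management group; 190 mildly malnourished children in 20 CNCs against 190 in 8; 50 infants in 20 CNCs against 50 in 8.

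**1. The plan's own figure.** n = (0.5×0.5 + 0.35×0.65)/0.15² × 10.5 = 0.4775/0.0225 × 10.5 = 222.8 (stated 222). Then 222 × 1.5 = 333, and 333 × 1.10 = 366.3 (stated 366). It reproduces.

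**2. Error of a child-level test.** If the true variance of the group difference is DE times the variance the test assumes, the actual two-sided error is 2 × (1 − Φ(1.96/√DE)). At DE = 1.5: 1.96/1.2247 = 1.600, so the error is 2 × (1 − Φ(1.600)) = 0.1095, about 11%.

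**3. Implied ICC.** 375/20 = 18.75 children per CNC. From DE = 1 + (m − 1) × ICC, ICC = 0.5/17.75 = 0.028.

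**4. Simulation under no effect.** With 20 CNCs per group, 375 children per group and ICC 0.028, the child-level chi-squared test rejected in 11.0% of runs and the child-level t test in 10.7%. A t test on CNC proportions, using the same simulated binary data, rejected in 4.9%.

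**5. Range for an assumed ICC, management comparison.**

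| ICC (assumed) | DE | Actual error |
|---|---|---|
| 0.01 | 1.18 | 7.1% |
| 0.028 (implied by 1.5) | 1.50 | 10.9% |
| 0.05 | 1.89 | 15.4% |

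**6. Preventive comparisons at ICC 0.028.** With equal numbers of children per group, the DE of the contrast under no effect is the mean of the two group values.

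| Group | Children per CNC | DE by group | Mean DE | Actual error |
|---|---|---|---|---|
| Mildly malnourished | 9.5 and 23.75 | 1.24 and 1.64 | 1.44 | 10.2% |
| Well-nourished infants | 2.5 and 6.25 | 1.04 and 1.15 | 1.09 | 6.1% |

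If 1.5 is applied directly to the mildly malnourished group, as the protocol does, that comparison is also at 11%. None of these figures includes a penalty for estimating between-CNC variation from 8 control centres.

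**7. Allocation within unions.** The protocol says the 5 CNCs in each of 8 unions are allocated between the two groups. Suppose the splits are 3:2, balanced to give 20 against 20, and a share s of the ICC lies at union level (s is an assumption; the protocol gives nothing on it). With total variance 1, the variance of the group difference is 8 × (1/20)² × s × ICC + 40 × (1/20)² × (1 − s) × ICC + (2/375) × (1 − ICC), against an assumed 2/375.

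| s | Variance ratio | Actual error |
|---|---|---|
| 0 | 1.50 | 11.0% |
| 0.25 | 1.39 | 9.7% |
| 0.50 | 1.29 | 8.4% |
| 0.75 | 1.18 | 7.2% |

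**8. Power once clustering is respected.** At DE 1.5, 375 per group is equivalent to 375/1.5 = 250 independent children, with power about 93% before dropout. The stated 333 is equivalent to 222, with power about 89%.

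**The case against.** The strongest objection is to the size. The 1.5 is a round planning factor with no ICC behind it, so 11% is a conditional figure. Allocation within unions would remove much of any union-level clustering from the contrast and bring the error down towards 7% to 10%. This stands. It cannot be settled from the text, because the allocation diagram is not shown and one sentence about the 5 CNCs per union is ambiguous; if whole unions were allocated, the inflation would be larger. The regression's covariates may also absorb some between-CNC variation, so the t test and chi-squared figures do not transfer directly to it.

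A second objection is that the section is brief, its covariate list is open-ended, and a statistical analysis plan that is not at hand might add a CNC term. This is weak. The protocol names specific tests that conflict with its own allocation; the listed covariates are child or household variables; and the t test and chi-squared test take no covariates. The preventive sample-size paragraph also says the cluster effect is dealt with by the factor of 1.5, although the management paragraph makes no such claim.

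A reader might infer two stronger points that the document does not support. One is that too-narrow intervals would falsely support non-inferiority of LINE. The protocol states no margin, no one-sided limit and no confidence interval for this comparison; under its stated rule, the excess error works against equal effectiveness. The other is that every comparison is inflated equally. The infant comparison, with few children per CNC, is barely affected at the implied ICC.

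**Conclusion.** The plan is wrong as written: whole CNCs are allocated, and only child-level tests are named. The main comparison of INE with LINE has a true error of about 11% in place of 5% if the protocol's design effect of 1.5 is right. With an assumed ICC of 0.01 to 0.05 the range is about 7% to 15%, and it is lower if CNCs are allocated within unions and some clustering is at union level. At the implied ICC of 0.028 the error is about 10% for mildly malnourished children and about 6% for well-nourished infants, in both cases before allowing for only 8 control CNCs. A flat statement that the error is 11% would go too far. That it exceeds 5% under any positive correlation within CNCs does not depend on the exact ICC. The point should be corrected before analysis.

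**What to change.** In Data Analysis, replace the child-level tests for between-group comparisons with an analysis that respects the CNC. Either of these will do:

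- one summary per CNC (proportion improved, mean weight gain), compared between groups; or
- a mixed model with a CNC random effect, union as stratum and the planned baseline covariates.

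Base the degrees of freedom on the number of CNCs. For an unstratified comparison of CNC summaries that is 20 + 20 − 2 = 38 for management and 20 + 8 − 2 = 26 for prevention. If GEE is preferred, add a small-sample correction; this matters most for 20 against 8. State how CNCs are allocated within unions, and report the ICC. Keep the factor of 1.5 in the sample size, described as protecting power only.

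The cost is revised wording, slightly more analysis work and wider intervals. No new data or children are needed, and under the protocol's own assumptions power stays near the planned 90%.
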